6.1. Data sources

6.1.1. Context and rationale for data sources

The overall ENCORE project uses data from a total four different oncology-specific electronic health records (EHR)-derived data sources: ConcertAI, COTA, Flatiron Health, McKesson/Ontada. For ENCORE, not all databases are available for each cancer indication and the names of the databases will henceforth be blinded and referred to as ENCORE DataBase (EDB) 1, 2, 3 and 4 (the numbering does not coincide with the above order of mention of the databases).

For this trial emulation, breast cancer-specific data are available for EDB1, EDB3 and EDB4. The fitness-for-purpose of the data for the given trial emulation were assessed and considered for the final selection of the databases.

Reason for selection: All considered databases draw from a comprehensive national sample of patients with cancer in the US with detailed EHR-derived information on the information necessary to study medication effectiveness in oncology.

Strengths of data source(s): Size and detailed clinical information on oncology-specific variables and outcomes (validated composite all-cause mortality sourced from different data sources^{8,9}).

Limitations of data source(s): General limitations across all data sources include missing data, potential lack of data continuity, heterogeneous data provenance, quality/heterogeneous ascertainment of mortality endpoint data and the variability in how line of treatment is captured and curated (a more comprehensive discussion of the data sources and approaches is provided in section 7. After a comprehensive assessment of all data sources regarding their fitness for the purpose of emulating the PALOMA-2 trial, EDB4 was found insufficient to be included in the main analysis for the following reasons.

- **Rationale for excluding of EDB4 from primary analysis:** Since the study identification period (10/01/2018–09/30/2023) began after the 2015 approval of palbociclib, patients who initiated palbociclib before 10/01/2018 were only included if they survived until the start of the study period, which may introduce selection bias due to left truncation.¹⁰
- For these reasons, only EDB1 and EDB3 will be used for the main analysis. However, EDB4 will be considered as part of a sensitivity analysis to observe the results in a setting which may be impacted by selection bias (see sensitivity analysis #11 in Table 8).

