6.6.7. Context and rationale for covariates

We identified a series of covariates that are strong prognostic factors for the outcome and auxiliary covariates which may be useful to impute missing data. Such covariates comprise demographics, covariates indicating disease-severity, cancer-specific covariates as well as pathological and genetic factors. In addition, selected labs and vitals are considered since they were shown to carry a high amount of prognostic information as described in Becker, Weberpals, et al.¹¹ For these variables, additional plausibility checks and transformations are carried out. In detail, labs and vitals are individually checked if they cross a certain biologically implausible threshold (e.g., a heart rate of 0) in which cases the values are set missing and imputed in a next step. These thresholds were compiled by experienced practicing physicians and medical oncologists and are listed in appendix **Table 8** and **Table 9**.

Note that not all covariates are available across all databases used for this trial emulation. In the analytical stage, the most comprehensive model will be fit for each database individually.

Table 5. Operational definitions of key covariates used for trial emulation.

Characteristic	Harmonized analysis variable name	R function to derive covariate (see pdf in appendix)	Details ¹	Variable encoding	Assessment window
Age at index date	dem_age_index	edbx_get_demographics()	Age measured at index date	Binary (<60, 65+); modelled continuously in ROPRO ¹⁰	[0;0]
Year of index date	c_year_index	De novo derived from dt_index	Calendar year in which patient initiated study treatment	Nominal (<2020, 2020+)	[0;0]
Family history	dem_family_history	edbx_get_demographics()	Family history of cancer. Not available in EDB1.	Logical (TRUE, FALSE)	[0;0] (no specific date is associated)
Race	dem_race	edbx_get_demographics()	Race categorized as in the original RCT	Binary (Asian vs non-Asian)	[0;0]
Ethnicity	dem_ethnicity	edbx_get_demographics()	Ethnicity	Hispanic, Non-Hispanic	[0;0]
Region	dem_region	edbx_get_demographics()	US region patient receives care in; if given on a state level, region is manually mapped (see Table 10)	Nominal (Northeast, South, West, Midwest)	[0;0]
Practice type	dem_practice	edbx_get_demographics()	Setting patient is receiving care at. Not available in EDB3 and EDB4.	Nominal (academic, community, academic & community)	[-inf;0]

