	
In subgroup analysis, multiple imputation, propensity score matching and balance assessment will be conducted within each subgroup separately. The treatment effect will be estimated for each stratum separately (stratum-specific effects).
 
 1. Age (<65, ≥65) 2. Region (North America, Europe, Asia/Pacific) 3. ECOG (0, 1) 4. Disease-free interval (De-novo metastatic, ≤12 months, >12 months) 
According to Slamon et al,⁶ the subgroup analyses are considered exploratory in nature and performed with no formal statistical testing.

Table 8. Sensitivity analyses – rationale, strengths and limitations.

	What is being varied? How?	Why? (What do you expect to learn?)	Strengths of the sensitivity analysis compared to the primary	Limitations of the sensitivity analysis compared to the primary
Sensitivity #1	Caliper matching on ROPRO prognostic score instead of propensity score	Matching patients on validated prognostic score may be more beneficial to control for (unmeasured) confounding	Matches patients on validated prognostic score that incorporates weights of key prognostic factors	Limited experience on how to optimally use prognostic scores and should be seen as an experimental sensitivity analysis
Sensitivity #2	Average treatment effect in the overlap population (ATO) weighting instead of matching	Weights that resemble the average treatment effect in the overlap population (ATO) create a clinical equipoise population which is comparable to an RCT	ATO weighting usually results in excellent balance and clinical equipoise	Estimates the average treatment effect among the overlap patients which may not be comparable to target population anymore
Sensitivity #3	SMR/ATT weighting instead of matching. Here symmetric trimming (i.e., setting all weights lower/higher than that at a given quantile to the weight at the quantile) of extreme weights may be considered with the quantiles chosen based on weight distribution and resulting balancing performance.	SMR weighting retains all patients and resembles the same estimand as matching	ATT weighting retains all patients	Patients with extreme weights after trimming may bias the analysis

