Sensitivity #4	Censoring date is changed to 3 months before data cut-off date	For all databases, information on mortality comes from different data sources which are updated asynchronously. To account for the potential lag of updated mortality information (ghost-time bias ³⁷), the censoring for patients without mortality event in the whole patient identification period will be moved to last sign of patients being alive/visit or 3 months before data cut-off date, whichever occurred earlier. ³⁸	Approach implements a more conservative censoring rule	Approach addresses ghost-time bias by censoring patients without a recorded death event earlier
Sensitivity #5	Delta imputation models for MNAR (tipping point analysis)	Primary multiple imputation analysis assumes MAR which	Estimates impact of deviations from MAR assumption on final	Delta parameters must be assumed and results are complex to interpret in

		may not hold for every covariate	treatment effect estimates for key covariates	multivariate missingness settings; just most important covariates or those with highest suspicion of being MNAR will be evaluated
Sensitivity #6	Re-weighting of strong risk factors and/or treatment effect modifiers distribution to match that of PALOMA-2	In the presence of effect modification, treatment effect estimates may be different if the distribution of strong risk factors/effect modifiers is different in the emulated cohort versus the trial cohort	Re-weighting adjusts for differences in distributions of key risk factors and/or treatment effect modifiers (see subgroup analysis in Table 7)	Re-weighting risk factors/potential effect modifiers to match the PALOMA-2 trial and simultaneously balancing them across treatment groups may be challenging due to differences in measurement
Sensitivity #7	Including patients who have had at least 1 visit 90 days prior to treatment initiation	EHR are often lacking data continuity, and this analysis uses the requirement of 1 visit as a proxy for continuous observation periods	Considers aspect of data continuity	There may be patients who are put on treatment immediately in which case they are falsely excluded

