Inclusion	Measurable disease as defined per RECIST v.1.1 (see Appendix 7) or bone-only disease (with bone lesions confirmed by CT, MRI or bone X-ray). Tumor lesions previously irradiated or subjected to other locoregional therapy will only be deemed measurable if disease progression at the treated site after completion of therapy is clearly documented.	Relevant	Limited	Limited	Limited	We are assuming that all subjects in RWD have measurable disease if they are receiving treatment
Inclusion	World Health Organization Performance Status of 0 to 1	Relevant	Limited	Limited	Limited	ECOG implementation possible; high % missingness likely
Inclusion	Adequate organ and marrow function defined as follows: ANC 1,500/mm3 (1.5 x 10 ⁹ /L); Platelets 100,000/mm3 (100 x 10 ⁹ /L); Hemoglobin 9 g/dL (90 g/L); Serum creatinine 1.5 x ULN or estimated creatinine clearance 60 mL/min as calculated using the method standard for the institution; Total serum bilirubin 1.5 x ULN (3.0 x ULN if Gilbert's disease); AST and/or ALT 3 x ULN (5.0 x ULN if liver metastases present); Alkaline phosphatase 2.5 x ULN (5.0 x ULN if bone or liver metastases present).	Limited relevance	Not implementable	Not implementable	Not implementable	High % missingness likely, more of a concern for safety issues
Inclusion	Resolution of all acute toxic effects of prior anti-cancer therapy or surgical procedures to NCI CTCAE version 4.0 Grade 1 (except alopecia or other toxicities not considered a safety risk for the patient at investigator's discretion).	Limited relevance	Not implementable	Not implementable	Not implementable	More of a concern for safety issues
Inclusion	Willingness and ability to comply with scheduled visits, treatment plan, laboratory tests, and other study procedures.	Limited relevance	Not implementable	Not implementable	Not implementable	Not applicable

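### Two of the four Table 7 subgroups do not fit the data or the missing-data plan: continental region in US-only databases, and ECOG strata that leave out patients with missing ECOG

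*Combined protocol and SAP*

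**What the plan says.** **Region.** Table 7 in Section 6.7.1 gives one of four subgroups as "Region (North America, Europe, Asia/Pacific". Section 6.1.1 describes the data differently: "All considered databases draw from a comprehensive national sample of patients with cancer in the US". Table 5 (Section 6.6.7) defines the region variable as "US region patient receives care in; if given on a state level, region is manually mapped", encoded as "Nominal (Northeast, South, West, Midwest". Table 10 (Section 10.4) maps US states to those four levels. No continent variable is defined.

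Sensitivity #6 (Table 8, sensitivity analyses) re-weights strong risk factors and/or effect modifiers to the distribution in PALOMA-2. For these it refers the reader back: "see subgroup analysis in Table 7".

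**ECOG.** Table 7 also lists ECOG 0 and 1 as subgroups and says that "multiple imputation, propensity score matching and balance assessment will be conducted within each subgroup separately". Section 6.7.1 counts patients with missing values as eligible when the cohort is built. For performance status, the table evaluating the trial's eligibility criteria (Excel appendix table 1) notes: "ECOG implementation possible; high % missingness likely". Section 6.7.1 justifies multiple imputation partly because it keeps all patients in the analysis.

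**The concern.** A subgroup analysis needs strata that contain patients and a rule that places every eligible patient in one of them. Region fails on the first count, ECOG on the second.

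The study asks how far the emulated effect agrees with the trial. Subgroup estimates and the re-weighting in Sensitivity #6 are among the tools for explaining disagreement. A region row that cannot be filled invites either an unexplained gap or an improvised substitute once results are known.

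For ECOG, the stated order of steps changes the analysis population without saying so. The primary analysis imputes ECOG. The ECOG subgroups would use only patients whose ECOG was recorded, so a difference between a subgroup and the main result could reflect who has ECOG recorded rather than effect modification. The plan reserves complete-case analysis for Sensitivity #9, where it states the stronger missingness assumption openly.

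**Working it through.** **Step 1: region, by comparison of sections.**
- Planned levels (Table 7): three continental groups.
- Available levels (Tables 5 and 10): Northeast, South, West, Midwest, all within the US.
- Result: Europe n = 0, Asia/Pacific n = 0, North America = the whole cohort. Two of three strata are empty by construction, and the third repeats the main analysis.

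**Step 2: ECOG, by order of operations.**
- Before imputation, a patient with missing ECOG has no stratum.
- Inside the ECOG 0 stratum, ECOG is 0 for everyone, and likewise for ECOG 1. Imputation within a stratum therefore never imputes ECOG and cannot bring such a patient in.
- Result: each stratum holds only patients with observed ECOG. The plan gives no rule for the others and does not say that they are dropped.
- By contrast, Table 5 models ECOG as binary (0, 1). Imputing ECOG in the full cohort would give every patient a stratum in each imputed dataset.

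**Step 3: the plan's own figures.** Section 10.3 gives power for the full matched sets only, at HR 0.92, alpha 0.05 and 50% exposed. With d events, power = Φ(√(d/4) × |ln 0.92| − 1.96), where |ln 0.92| = 0.0834.
- EDB1, d = 1021: 15.98 × 0.0834 = 1.332; Φ(−0.628) = 0.265 (plan: 0.27).
- EDB3, d = 331: 9.10 × 0.0834 = 0.759; Φ(−1.201) = 0.115 (plan: 0.11).

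Both agree within rounding, so the event counts are used below.

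**Step 4: size of the ECOG loss.** The documents give no ECOG missing share, so m = 20%, 40% and 60% are assumptions. Further assumptions are that events and matched pairs fall in proportion to patients and that observed ECOG splits 50/50.
- With 1:1 matching, SE(log HR) ≈ √(4/d). Losing a share m turns d into d(1 − m), so the CI on the log scale widens by 1/√(1 − m).
- Events per stratum = d(1 − m)/2. The 95% limits are HR divided and multiplied by exp(1.96 × √(4/events per stratum)).
- Example, EDB1 at 40%: 1021 × 0.6/2 = 306; √(4/306) = 0.114; exp(1.96 × 0.114) = 1.25.

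| Assumed missing | CI width ratio | EDB1: in neither stratum (of 1812) | EDB1: events per stratum | EDB1: CI multiplier | EDB3: in neither stratum (of 610) | EDB3: events per stratum | EDB3: CI multiplier |
|---|---|---|---|---|---|---|---|
| 0% | 1.00 | 0 | 510 | 1.19 | 0 | 166 | 1.36 |
| 20% | 1.12 | 362 | 408 | 1.21 | 122 | 132 | 1.41 |
| 40% | 1.29 | 725 | 306 | 1.25 | 244 | 99 | 1.48 |
| 60% | 1.58 | 1087 | 204 | 1.32 | 366 | 66 | 1.62 |

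The ratio compares the complete-case subgroup with one in which every patient's ECOG is known. Imputed ECOG is not known ECOG. Between-imputation variance would take back part of the gain, so under these assumptions the ratios are upper bounds.

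**The case against.** **The ECOG subgroup would run.** A reader might infer that it cannot be executed. It can: the code would return estimates for patients with observed ECOG. The defect is an unstated change of population, not an impossible analysis.

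**Missing ECOG may not be retained.** The operational definitions (Excel appendix table 2) and Table 2 allow missing values explicitly for ER, while the ECOG entry names only 0 or 1. If patients with missing ECOG are in fact excluded, the ECOG half of this point falls away. The attrition diagrams are not readable in the text available, so the count cannot be checked. The general rule in Section 6.7.1 and the expectation of high missingness favour retention, but the two places need reconciling.

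**Sensitivity #6.** A reader might infer that it cannot be completed. The documents do not support that. It has no variable list, its and/or wording leaves the choice of factors open, and region enters only through the cross-reference to Table 7. Age, ECOG and disease-free interval remain usable. It needs one clarifying sentence.

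**Region still offers one comparison.** It would be too strong to say that region yields nothing to set against the trial. The full-cohort estimate is the natural counterpart of the trial's North America stratum. Using the four US regions instead would be feasible, but those strata would match none of the continental groups in Table 7.

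**Strata that do not sum to the primary matched set.** This is not evidence of the defect. Matching is redone within each stratum, so the sets need not add up even with complete ECOG.

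**Imputing within strata has a merit.** It lets covariate relations differ by subgroup. Imputing in the full cohort can dilute subgroup differences if the model cannot represent them. This stands, and the fix must deal with it.

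**Conclusion.** The region part holds without conditions: two of three strata are empty and the third is the main analysis.

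The ECOG part holds if patients with missing ECOG stay in the cohort, as the general rule in Section 6.7.1 says. The ECOG subgroups then become complete-case on ECOG, against the plan's own reason for imputing. The loss of precision is at most about 12%, 29% or 58% in CI width at an assumed 20%, 40% or 60% missing. None of these is an expected value, because the documents give no share. The selection problem does not depend on that share, as long as some ECOG values are missing.

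The consequences are limited. Table 7 calls the subgroups exploratory, without formal testing, and the primary hazard ratio, the pooling across databases and the stated power are untouched. The changes should be made before the analysis, but they do not bear on the main conclusion.

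**What to change.** 1. **Table 7, region.** Remove region as a subgroup. State that the trial's Europe and Asia/Pacific strata cannot be emulated and that the full-cohort estimate is the counterpart of its North America stratum.
2. **Table 8, Sensitivity #6.** List the factors to be re-weighted and state that region is not among them.
3. **Table 7, ECOG and any other partly missing subgroup variable.** Impute once in the full cohort, split each imputed dataset by ECOG, match and estimate within stratum, and pool with Rubin's rules. Table 7 already puts exposure and outcome in the imputation model. Add how it will allow treatment-by-ECOG and outcome-by-ECOG structure, so that subgroup differences are not diluted. Check whether disease-free interval has missing values too; the documents do not say.
4. **Eligibility.** Reconcile the rule in Section 6.7.1 that keeps missing values with the ECOG entry in the operational definitions, and report the number with missing ECOG per database.

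If the current order of steps is kept, the least that is needed is a sentence saying that the ECOG subgroups are limited to patients with observed ECOG.

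The cost is a few lines in Tables 7 and 8 and a small amount of recoding within the existing workflow of matching inside each imputed dataset. The ECOG subgroups would then rely on missing at random for ECOG, which the primary analysis already assumes.

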To estimate the treatment effects for palbociclib plus letrozole using propensity score matching across imputed datasets we will apply the “within” approach using the “MatchThem” R package.^{30,31} That is, propensity score matching and the estimation of the treatment effect are performed in each imputed dataset separately and resulting treatment effect estimates are combined using Rubin’s rule. In this study, this will be implemented by matching eligible patients on their propensity to initiate palbociclib plus letrozole using a 1:1 nearest neighbor matching algorithm without replacement and a caliper of 1% of the standard deviation of the propensity score. The resulting covariates balance will be assessed by computing and visualizing ASMDs before and after matching across datasets. As compared to a single dataset matching approach, this can lead to a range of ASMDs per covariate due to random variation across imputed datasets for which an example (using simulated data) is illustrated in Figure 3. If sufficient balance can be established, a Cox proportional hazards regression model will be fit to estimate the marginal average treatment effect in the matched population. Since in most databases there are more palbociclib-plus-letrazole patients than patients in the control arm, the estimand will rather correspond to the ATC than the ATT. Confidence intervals will be estimated using cluster-robust standard errors.³² As a secondary endpoint, we will additionally estimate the median OS survival time difference between the two exposure groups using the Kaplan-Meier method. It should be noted that due to administrative and de-identification purposes, the date of death is often only available at the month- or year-granularity level, in which case the date of death will be imputed to the 15th of a month or July 2nd of a year, respectively (depending on the database). In rare cases, this can lead to negative/implausible follow-up times if the date of death is very close to the index date. These patients will be excluded from the analysis.

The final hazard ratio and median OS survival time difference estimates for each database will then be combined using Rubin’s rule.^{29,33} To arrive at a single estimate across databases, the final estimates will be summarized through a meta-analytic fixed effects model.³⁴ A summary of the analytic approach is summarized in Table 7 and an example workflow with simulated data and annotated code can be found [here](#).

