A. Primary analysis

Table 7. Primary, secondary, and subgroup analysis specification

Hypothesis:	Initiation of palbociclib plus letrozole decreases the hazard of all-cause mortality as compared to initiation of letrozole alone
Exposure contrast:	Initiation of palbociclib plus letrozole vs letrozole alone
Primary outcome:	Time to all-cause mortality (OS)
Secondary outcome:	Time-to-next-treatment (TTNT) defined as a composite outcome of all-cause mortality or adding or switching to a next-line treatment. ^{35,36}
Databases used:	EDB1 and EDB3 (primary analysis), EDB4 (sensitivity analysis)
Time period:	From 2015 (approval year for palbociclib) - 2022 (publication of final OS outcome results for competitor ribociclib) ⁷
Analytic software:	R 4.3.2. Version control of code and R packages will be established through git and Posit package manager, respectively. All packages are frozen to their most recent version as of April 25, 2024.
Model(s): (provide details or code)	See example code here . The annotated code for the trial emulation will be hosted at https://drugapi.gitlab-pages.partners.org/encore/paloma2-nct-01740427/ (access only through MGB network for authorized personnel)
Confounding adjustment method	Name method and provide relevant details, e.g. bivariate, multivariable, propensity score matching (specify matching algorithm ratio and caliper), propensity score weighting (specify weight formula, trimming, truncation), propensity score stratification (specify strata definition), other.
	1:1 propensity score nearest neighbor matching without replacement and a caliper of 1% of propensity score standard deviation
Missing data methods	Name method and provide relevant details, e.g. missing indicators, complete case, last value carried forward, multiple imputation (specify model/variables), other.
	Multiple imputation by chained equations using a random forest imputation model across all covariate types. The number of imputed datasets will be determined by the average proportion of missing values across all partially observed covariates. Imputation models will include all variables of the substantive model, i.e., exposure, outcome, confounders/prognostic factors and additional auxiliary covariates.
Subgroup Analyses	List all subgroups

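### Sensitivity #3 uses ATT weights as having the same estimand as matching, but section 6.7.1 places the matched estimand nearer the ATC wherever palbociclib patients are the majority

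*Combined protocol and SAP*

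**What the plan says.** The primary analysis in section 6.7.1 and Table 7 is "1:1 propensity score nearest neighbor matching without replacement and a caliper of 1% of propensity score standard deviation". A Cox model is then fitted to "estimate the marginal average treatment effect in the matched population". The section names the population this describes: since "in most databases there are more palbociclib-plus-letrazole patients than patients in the control arm", it says "the estimand will rather correspond to the ATC than the ATT".

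Table 8 (sensitivity analyses) specifies Sensitivity #3 as "SMR/ATT weighting instead of matching" and gives as its rationale "SMR weighting retains all patients and resembles the same estimand as matching". The only limitation listed in that row is "Patients with extreme weights after trimming may bias the analysis".

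Two other rows bear on the point. Row #2 (overlap weighting, ATO) warns that its target population may differ from the intended one. Row #6 accepts that the target population can matter: "In the presence of effect modification, treatment effect estimates may be different if the distribution of strong risk factors/effect modifiers is different". None of Sensitivity #1 to #12 uses ATC weights.

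**The concern.** ATT weights standardise the letrozole-alone patients to the covariate mix of the palbociclib initiators. By the plan's own account, the primary match mostly describes the covariate mix of the letrozole-alone patients. Row #3 is therefore presented as a change of method with the target held fixed, when in a treated-majority database both change together.

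The interpretation of a discrepancy is at stake. The study is meant to judge concordance with a trial OS hazard ratio of 0.96 (95% CI 0.78 to 1.18, section 4), so shifts of a few percent will be discussed. Someone relying on the rationale in row #3 would put a shift between #3 and the primary result down to matching versus weighting. If the effect varies across patients, the shift could come wholly or partly from the change of population.

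**Working it through.** **The plan's own figures.** The documents give no figure for the estimand. The only design figures are the power values in section 10.3, and the point does not depend on them. They reproduce with Schoenfeld's formula, two-sided alpha 0.05, 50% exposed, HR 0.92: power = Φ(√(0.25 × events) × |ln 0.92| − 1.96).
- EDB1, 1021 events: Φ(15.98 × 0.0834 − 1.96) = 0.265 (stated 0.27).
- EDB3, 331 events: Φ(9.10 × 0.0834 − 1.96) = 0.115 (stated 0.11).

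**Step 1: what each analysis targets.** PS is the probability of starting palbociclib plus letrozole.
- ATT (SMR) weights: treated = 1, controls = PS/(1 − PS). The target is the treated population.
- ATC weights: controls = 1, treated = (1 − PS)/PS. The target is the control population.
- 1:1 matching without replacement cannot keep more pairs than the smaller arm allows. If treated patients are the majority, most controls can find a partner and many treated patients are discarded, so the matched set resembles the controls. This is the plan's own reasoning for its ATC statement.

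The rationale in row #3 therefore fits only a database where controls are the majority.

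**Step 2: size under assumed effect modification by age.** All inputs are assumptions. The share of younger patients is taken to be 20 points higher in the palbociclib arm, and log HRs are averaged over two age strata:

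ATT HR / ATC HR = exp(0.20 × ln(HR younger / HR older))

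- HRs 0.85 and 1.05: exp(0.20 × (−0.2113)) = 0.959, about 0.96.
- HRs 0.90 and 1.00: exp(0.20 × (−0.1054)) = 0.979, about 0.98.
- Equal HRs: exp(0) = 1, no shift.

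**Step 3: where the matched set lies.** This simulation also rests entirely on assumed inputs: 400,000 patients, one standard-normal covariate, a logistic PS with slope 0.8, mean log HR = ln 0.96, and log HR changing by 0.15 per SD of the covariate. Tight 1:1 matching is approximated by weights min(PS, 1 − PS). Entries are exp(mean log HR) in each target population.

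| Treated share | Controls / treated matched | Matched | ATT | ATC | ATO |
|---|---|---|---|---|---|
| 0.39 | 54% / 85% | 0.991 | 1.023 | 0.921 | 0.980 |
| 0.50 | 71% / 71% | 0.960 | 1.011 | 0.911 | 0.960 |
| 0.65 | 89% / 48% | 0.920 | 0.997 | 0.896 | 0.933 |
| 0.74 | 96% / 33% | 0.897 | 0.987 | 0.886 | 0.915 |

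Relative to the matched set:
- Share 0.65: ATT is 0.997/0.920 = 1.08 and ATC is 0.896/0.920 = 0.97.
- Share 0.74: ATT is 0.987/0.897 = 1.10 and ATC is 0.886/0.897 = 0.99.
- Share 0.39: the order reverses, with ATT 1.023/0.991 = 1.03 and ATC 0.921/0.991 = 0.93.

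With a constant effect, every entry is 0.960.

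**The case against.** The strongest reply is that the mismatch is conditional and partly covered already. Much of that stands.

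- **Arm sizes.** The plan refers to most databases, not all, and pre-matching counts appear only in figures not reproduced in the text. A reader might infer that ATC weights belong in every database. The documents do not support that: where letrozole-alone patients are the majority, ATC weights would recreate the mismatch in reverse, as the 0.39 row shows.
- **Not exactly the ATC.** A reader might take the match to be the ATC outright. The plan says only that it corresponds to the ATC rather than the ATT, and the tight caliper can drop controls without a close partner.
- **Sensitivity #2 helps.** ATO weighting targets a population near the matched one. In the simulation it is closer to the matched set than ATC at share 0.65 (0.933 and 0.896 against 0.920), though not at 0.74 (0.915 and 0.886 against 0.897). Row #3 is thus not the only check on the adjustment method.
- **Agreement is informative.** It would be too strong to say that agreement between #3 and the primary result carries no weight. Agreement across the matched, ATO and ATT results would support robustness to both method and population. Disagreement is what becomes ambiguous.
- **Other inferences.** One might suppose that only a few letrozole-alone patients resemble palbociclib patients, that extreme weights will certainly be trimmed, or that the pooled primary estimate mixes ATT and ATC. Propensity distributions are not in the text. Trimming is only an option in row #3. The exception to most databases could be EDB4, which is outside the primary analysis.

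None of this reconciles the ATC statement in section 6.7.1 with the rationale in row #3.

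**Conclusion.** The point holds in a limited form. Both statements are current text and nothing else in the plan reconciles them. In any database where palbociclib-plus-letrozole patients outnumber letrozole-alone patients, the rationale for Sensitivity #3 is wrong, and unlike row #2 it carries no warning about the target population.

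Confidence is high for the textual conflict. The numerical consequence is illustrative: an ATT/ATC ratio of HRs of about 0.96 or 0.98 under the two assumed age patterns, and essentially none if the effect is homogeneous. The documents supply neither the age-specific HRs nor the 20-point difference. The first ratio happens to equal the trial's OS hazard ratio of 0.96, but that should not be read as a predicted bias. The effect is on how a secondary analysis is interpreted; the primary analysis and the stated power are untouched.

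**What to change.** 1. In section 6.7.1, state for each database which arm is larger before matching and which estimand the match therefore approximates.
2. In databases where treated patients outnumber controls, use ATC weights in Sensitivity #3 (letrozole alone = 1; palbociclib plus letrozole = (1 − PS)/PS) as the closer like-for-like check. Note that, with the caliper, the match is only approximately the ATC.
3. If ATT weighting is kept in those databases, delete the claim that it shares the estimand of matching and list the different target population as a limitation, as row #2 already does for ATO.

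The cost is one weight definition and a few sentences in section 6.7.1 and Table 8. No new data are needed.
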